Methionine	disease intermediary	Metabolite Laboratory, Inc
Cystathionine	disease intermediary	Metabolite Laboratory, Inc
Cysteine	disease intermediary	Metabolite Laboratory, Inc
S-adenosylmethionine	disease intermediary	[name] Anesthesiology Laboratory
S-adenosylhomocystiene	disease intermediary	[name] Anesthesiology Laboratory
Dimethylglycine	compliance of standard Tx	Metabolite Laboratory, Inc
Betaine	compliance of standard Tx	[name]/UCD
Serum amino acids (includes taurine)	compliance of experimental Tx	Denver Genetic Laboratory - Biochemical Genetic Laboratory
Taurine	Pharmacokinetics	[name], Anesthesiology Laboratory
Platelet aggregation	Coagulation assessment	local lab*
Lipoprotein A	Atherosclerotic disease marker	Mayo
11-dehydroTXB2, 2,3-dinor-TXB2, urine	Coagulation assessment	[name]/UCD
CBC	Safety	local lab**
CMP	Safety	local lab**
Lipid panel	Safety	local lab**
Triglyceride level	Safety	local lab**
pregnancy, urine	Safety	local lab**
Cystathionine β -synthase molecular (CBS)	Genotype	Denver Genetic Laboratories – Molecular Laboratory
Plasma, serum and urine freeze - 70, save		[name]/UCD
Estradiol/Progesterone (Females)	Menstrual cycle timing for	UCH CTRC

only)	FMD interpretation
-------	--------------------

* For Colorado, this will be University of Colorado Hospital Laboratory

** For Colorado, this will be Children's Hospital Colorado

	THUR* Day 1	FRI Day 2 8 AM	FRI Day 2 12 PM	TUE Day 6 8 AM	TUE Day 6 After 8 AM
Informed consent	X				
Intake sheet (see appendix)	X				
Adverse Event/Compliance Sheet (see appendix)†		X		X	
Medical History	X				
Physical exam	X			X	
Endothelial function studies	X				X
DEXA scan	X				
Blood Luminex, CRP, myeloperoxidase, TGF-β (CTRC)	X	X	X	X	
Urine isoprostane, dityrosine		X		X	
Glutathione	X	X	X	X	
Lipoprotein A		X			
CBC, CMP, Lipid panel		X		X	
Estradiol/Progesterone (Females only)	X‡	X‡			
Urine pregnancy tests	X				
Superoxide dismutase, TBARS, Elisa, ([name])	X	X	X	X	
Homocysteine and metabolites (Metabolite Inc)	X	X	X	X	
Betaine ([name])	X	X	X	X	
Serum amino acids (Biochemical Genetics)	X	X	X	X	
Plasma taurine	X	X¶	X¶	X	

Platelet aggregation studies (local lab)		X		X \bar{T}	
ThromboxaneB2 metabolites , urine		X	X	X	
Cystathionine beta-synthase molecular studies	X				
Plasma, serum and urine to freeze and save to include 1.0 ml EDTA plasma on the second day of the study	C	C	C	C	

*Day one of study will typically be on a Thursday, exceptions may exist

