† The adverse event survey will also be administered over the phone one to two weeks after study completion

X = collected and analyzed

C= collected and stored for possible studies during study period

¶ = collected before administration (time 0), and after 30 min, 1, 2, 4, 6, 8, and 12 hours.

‡ = collection can occur on Day 1 or Day 2 based upon site maximum blood volume

T̄= will not be collected if site maximum blood volume is reached

Practical Aspects: Samples not obtained for safety reasons will be batched to avoid inter-day variation. Analysis will be done at midway point and at study end. All samples will be stored at – 70 °C before being processed. Accurate SAM and SAH determination necessitates special handling of specimens and will be done in accordance with directions from assaying laboratory. The processing and freezing of samples for these studies will be done by the local laboratory in collaboration with the CTRC. The laboratory will be notified of anticipated samples per local standards. Accurate platelet aggregation studies necessitate that samples be analyzed within 3 - 4 hours of collection. In addition, platelet aggregation studies are sensitive to sample handling as sheer stress promotes platelet aggregation. Therefore, the samples for this study will be hand carried by study personnel (PI or assistant) to the main laboratory where they will be analyzed. Finally, collection of samples for platelet aggregation, should a heparin lock be in place, will be done in accordance to standard methods used for drawing coagulation studies, to avoid any potential confounding impact from heparin. All platelet aggregation studies will be scheduled with the local laboratory in advance in accordance with their protocol. For all draws from the heparin lock, specimens will be drawn per nursing protocol, and if not contraindicated at the time, the waste will be returned to the patient. A stopcock is used to decrease the risk of infection with returned blood. The line will be flushed with 0.9% normal saline and/or heparin as needed based on laboratory testing to be done. Flushing will use the Turbulent (push/pause) method to wash out any infusate or blood from the catheter. Samples for the 2,3-dinor-8-isoprostaglandin-F2 α are collected in the morning, which reduces intraperson variation, and stored at – 70 degrees Celsius until analysis (Zhang et

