It is anticipated that the biomarkers of oxidative stress and inflammation will be increased above the norm in participants and the degree of elevation will be related to Hcy levels. A decrease in the elevation of the biomarkers is anticipated following treatment with taurine. It is also anticipated that FMD studies will be abnormal in participants and that improvement will be seen following taurine supplementation. We anticipate that platelet aggregation studies will be normal, but that markers of generalized activation of platelets, thromboxane B2 metabolites, are elevated, and will reduce with treatment. Bone mineral density Z-scores will be related to baseline TNF- α levels.

J. Potential Problems:

1. Recruitment: Given the rarity of the disorder, our potential participant sample volume is low. Geographic and economic issues may make it difficult for some

potential subjects to participate in the study. Low participation in the study might impact the statistical analysis of data. Should insufficient patients be recruited locally, then advertisement through national organization will be done to increase participation. Of note, while there is one report of Vitamin C supplementation ameliorating endothelial dysfunction in individuals with CBSDH, its use has not been widely investigated and use of Vitamin C to treat homocystinuria is not standard of care. We therefore do not anticipate this excluding criteria to markedly effect recruitment.

Patients with prescribed salicylate (such as Aspirin) therapy will not have this discontinued but will be excluded from the platelet function studies. We anticipate that this will impact up to 25% of the recruited population. A recruitment of 12 patients will likely provide a minimum of 8 patients in which this clinically relevant measure can be analyzed. Should the percentage of patients taking platelet aggregation inhibitors exceed our anticipated number, then we will plan to extend the study to increase the number of patients to be enrolled. Similar considerations are for use of cGMP phosphodiesterase 5 inhibitors (such as Viagra) and exclusion of FMD studies, although we doubt that the rate of patients taking this medication in our young age group would be as high as 25%. Overall, our goal is to recruit 8 patients that participate in all aspects of the study and are treated at the target dose of 150 mg/kg/day (maximum 10 g/day).

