Analysis plan: The mean and standard deviation of TNF- α and TBARS at baselines and on therapy will be calculated, and the changes from baseline to therapy times will also be calculated and reported along with 95% confidence intervals. One-sample t-test will be used to test if the changes are significantly different from zero for both TNF- α and TBARS.

II. Secondary outcome measures: exploratory studies of other biomarkers of oxidative stress and inflammation, relationship to metabolites and to markers relevant of symptomatology

- A. Other biomarkers of oxidative stress and inflammation: A similar analysis as outlined above for TNF- α and TBARS will be done for the exploratory biomarkers of oxidative stress and inflammation. Because of the multiple comparisons in the many biomarkers, an adjustment of p-values will be done (such a Bonferroni or given the exploratory nature, a more relaxed method such as a family wise approach (false discovery rate) may be used). The findings will be used to generate new hypotheses for further study on independent datasets.
- B. Relationship to metabolites: For the relation to metabolites, the biomarkers listed in Table 1 will be correlated with total Hcy concentration using a Spearman's rank correlation coefficient, since the Hcy values are not likely to be normally distributed.
- C. Relationship to pathophysiologically relevant parameters of major symptomatology: For the evaluation of endothelial function abnormalities in CBSDH patients and its mitigation with taurine supplementation, the percent change in brachial artery diameter and the percent change in brachial artery flow induced by hypoxemia, will be compared between pre-treatment and after 4 days treatment. A paired t-test will be calculated to test if the percent change is significantly different from zero. To test whether platelet aggregation is mitigated by taurine supplementation, percent aggregation will be compared pre-treatment and at day 4 post-treatment using a paired t-test. Also, urine levels of thromboxane B2 metabolites will be similarly compared. To relate the bone mineral density to TNF- α levels, the Z-score of the BMD will be related to pre-treatment TNF- α levels and the correlation assessed using a Spearman or a Pearson product moment correlation coefficient, depending on the evaluation of normality of distribution.

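### The schedule names the Day 6 platelet sample, half of a planned before-after pair, as the only blood sample to omit at a site's volume limit, and does not mark the spare frozen aliquots

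*Combined protocol and SAP*

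**What the plan says.** The visit schedule in Section 5.H plans platelet aggregation twice: on Day 2 at 8 AM with a plain X, and on Day 6 at 8 AM with an X and a barred-T footnote. The footnote says that this sample "will not be collected if site maximum blood volume is reached". No other row carries it.

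One other footnote mentions the same limit. For estradiol and progesterone, "collection can occur on Day 1 or Day 2 based upon site maximum blood volume", so that draw may move but is not dropped.

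The spare-sample row reads "Plasma, serum and urine to freeze and save to include 1.0 ml EDTA plasma on the second day of the study". It is marked C on Day 1, at both Day 2 times and on Day 6, with no volume footnote. The key gives C as "collected and stored for possible studies during study period", and the assay table in the same section lists no purpose for these samples.

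For the analysis, Section 5.K.II.C states that "percent aggregation will be compared pre-treatment and at day 4 post-treatment using a paired t-test". Section 5.J, item 1, adds that "our goal is to recruit 8 patients that participate in all aspects of the study", at the target dose.

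The text above the blood-volume table (Blood Draws During Study Period) says that volumes will be reduced if limits are exceeded. It gives no order in which samples give way.

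**The concern.** The one sample singled out for omission has a planned test, while samples kept for unspecified use are not mentioned. Mitigation of altered aggregation by taurine is a stated hypothesis (Section 2), and its only planned test needs both time points. When the footnote applies, that test loses the patient.

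There is not much slack. Section 5.J expects up to 25% of patients to be excluded from the platelet studies because of prescribed salicylate. It provides for extra enrolment if platelet-inhibitor use is higher than expected, with similar considerations for phosphodiesterase 5 inhibitors, but not for samples lost to blood volume.

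**Working it through.** **1. Blood volume (table under Blood Draws During Study Period).**
- Through Day 2: 1.5 + 21.2 + 44.2 + (3 × 0.5) + 15.2 + (3 × 0.5) = 85.1 mL.
- Adding the Day 6 visit: 85.1 + 39.2 = 124.3 mL. This matches the table's running total. The text above the table says 121.5 mL, which is 2.8 mL less.

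**2. What kind of limit the footnote implies.** The documents do not define the site maximum. Day 6 takes 39.2 mL, less than the Day 2 8 AM draw (44.2 mL) or the whole of Day 2 (62.4 mL). A fixed cap per draw or per day would therefore bind on Day 2 first. A footnote placed only on Day 6 makes best sense for a cumulative limit. On that reading, the baseline platelet sample has already been taken when the limit is reached.

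**3. Weight at which a cumulative limit binds.** Threshold weight = total volume / limit per kg.
- At 5 mL/kg, the protocol's own 8-week figure: 124.3 / 5 = 24.9 kg. The protocol's 30 kg index child has 30 × 5 = 150 mL available and does not reach it.
- At 3 mL/kg for the whole study (an assumption; the protocol uses 3 mL/kg for a single draw): Day 6 would cross the limit for weights between 85.1 / 3 = 28.4 kg and 124.3 / 3 = 41.4 kg.

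**4. Patients available for the platelet pair.** The protocol expects at least 8 of 12. Its 25% exclusion gives 12 × 0.75 = 9, which agrees. Two further losses would leave 7.

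**5. Effect of losing pairs.** Section 5.K.I.B gives a power table for 8 pairs, paired t-test, one-sided 0.05. Power = P(T > t), where t is the 0.95 quantile of the t distribution with n − 1 degrees of freedom, and T is noncentral t with noncentrality d√n. For n = 8 this gives 0.801, 0.899 and 0.950 at d = 0.98, 1.15 and 1.30, against the stated 0.80, 0.90 and 0.95. The table is reproduced.

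| Pairs | Power at d = 0.98 | d detectable with 80% power |
|---|---|---|
| 8 | 80.1% | 0.98 |
| 7 | 74.0% | 1.07 |
| 6 | 66.2% | 1.19 |

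The protocol made this calculation for TNF-α and TBARS, so its use for aggregation is illustrative. The number of pairs lost is also an assumption.

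**6. Volume that the spare aliquots would free.** The 4-hour draw on Day 2 is 15.2 mL and covers the research assays plus the C samples. Day 6 adds the safety and platelet samples to the same list: 39.2 − 15.2 = 24.0 mL. The C share is an unknown part of the 15.2 mL. Only 1.0 mL of EDTA plasma on Day 2 is itemised, and part of the row is urine. Whether dropping the aliquots saves the platelet sample cannot be computed.

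**The case against.** The strongest reply is that putting aggregation last is a reasonable priority. Section 5.K.II treats it as a secondary, exploratory measure, although Section 5.A lists it under the primary outcome measures. The Expected Results text anticipates normal aggregation and looks for the taurine effect in thromboxane metabolites, which are urinary and keep their Day 2 and Day 6 pair. The blood tests competing on Day 6 include TNF-α, TBARS and the safety panel. This justifies ranking aggregation below those tests. It does not justify leaving it behind aliquots with no planned analysis.

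Several stronger readings are tempting, but the documents do not support them:
- **A reader might infer that the baseline platelet draw is wasted without its pair, so that both should be omitted.** It is not wasted. Section 2 also hypothesises that aggregation is altered in these patients, and Sections 5.A and 5.G relate biomarkers and metabolites to platelet function. The Day 2 value serves both.
- **A reader might infer that the loss will be common.** The site limit has no figure, the index child stays within 5 mL/kg, and the first four patients are adults.
- **A reader might take the limit as stated to be cumulative.** That is an inference. Moving the hormone draw between Day 1 and Day 2 would not change a cumulative total, so the same phrase there suggests a per-day or per-draw cap.
- **A reader might infer that the spare aliquots are protected.** They only lack the omission mark. The general clause on reducing volumes lets a site trim them, but does not say that they go first.
- **A reader might quote the two-sided change, from 1.16 to 1.43 SD.** The protocol's paired power basis is one-sided, and Section 5.K.II.C gives no sidedness for aggregation.

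**Conclusion.** The point holds as a small matter of sample priority. The schedule names one blood sample for omission, that sample completes a planned pair, and spare aliquots without a planned analysis are not placed ahead of it in the order of sacrifice. The damage is confined to the paired aggregation test.

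The size is uncertain. Going from 8 to 6 pairs would raise the detectable effect by 1.19 − 0.98 = 0.21 SD, but no document says how many pairs would be lost. Nor need two losses bring the count below 8: if 16 patients are exposed, two of them at the lower starting dose, then 14 × 0.75 = 10.5 remain after the expected exclusions. The conclusion rests on reading the missing footnote as no stated priority for the aliquots, and on a limit that first binds on Day 6.

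**What to change.** Reword the barred-T footnote to set an order. Before the first Day 1 draw, compare the patient's projected total with the site limit. If it is too high, drop the C blood aliquots first, at all visits. Omit the Day 6 platelet sample only if the total is still above the limit. Keep the baseline platelet draw in either case. The site limits themselves do not change.

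The cost is a wording change, a volume check using the weight already taken on visit day one, and fewer stored samples in small patients. Because the aliquot volumes are not itemised, the change may not rescue every pair. Listing them beside the platelet volume in the blood table would let each site see whether it does.

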Taken together, these observations indicate that dietary supplementation with taurine has significant therapeutic potential for treating CBSDH in humans. With its low-cost and low risk of side-effects, we propose investigation of taurine as an adjuvant therapy for betaine supplementation and methionine restriction.

Preliminary data from human CBSDH patients poorly compliant with standard therapy showed elevations of TNF- α (39.36 ± 4.85 pg/ml in un- or poorly treated and 19.33 ± 5.56 pg/ml in treated patients, versus controls 1.89 ± 0.53 pg/ml, $N = 10$, $p < 0.0001$) and TBARS (4.08 ± 0.56 nmol/ml in un- or poorly treated and 2.92 ± 0.38 treated patients, versus controls 2.23 ± 0.33 nmols/ml, $N = 10$, $p < 0.0001$ and < 0.0027 respectively). Cytokine profiling confirmed significant elevations in TNF- α , and the inflammatory cytokines IL-1 α and IL-1 β . Study subjects provided informed written consent for COMIRB protocol number 00-359.

5. Research Design and Methods

A. Overview - Brief Summary of Study Rationale:

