Patients taking platelet aggregation inhibitors such as salicylate on a PRN basis that are unwilling or unable to stop taking the medication for the study period to include the two week washout period will be excluded from the study for the impact on platelet function but will participate in the remainder of the study

2. Normal values: Normal values are available for nearly all measurements. Normal values are being developed by the CTRC laboratory for the Luminex panel of inflammatory markers and for TGF-beta.. Normal values for FMD studies will be developed from patients previously analyzed in the adult CTRC using the same methodology as discussed with [name].

K. Statistical Sampling, Sample Size and Analytical Plan

This study benefits from the statistical assistance provided through the CCTSI. The protocol was reviewed by biostatistician [name]. The services of [name] will be retained through the study.

I. The primary efficacy outcome parameters (Aim 2) are TBARS and TNF- α . For each of these two parameters, there are two questions:

- A. Is the biomarker elevated in the untreated patient compared to control?
This question is required to validate the preliminary data.
- B. Does the biomarker decrease following treatment with taurine, after 4 hours treatment (immediate response) and after 4 days of treatment (short term treatment)?
This question evaluates the impact or treatment on the primary outcome markers

Sample size and statistical power consideration:

A. Is the biomarker (TNF- α , TBARS) elevated in CBSDH patients? Hypothesis 1 states that extracellular biomarkers of oxidative stress and inflammation in CBSDH patients will be increased compared with control patient values. The proposed study will include mostly patients who are untreated or poorly treated (non-compliant patients) for conventional

treatment, but can also have treated patients. To be conservative, we will use the preliminary data from the treated patients to power the study.

For TNF- α , preliminary data showed a mean of 19.33 ± 5.56 pg/ml in CBSDH conventionally treated patients compared with a mean in controls of 1.89 ± 0.53 pg/ml. When the sample size is 8, a single group t-test with a 0.05 two-sided significance level will have 99% power to detect the difference between a null hypothesis mean TNF- α of 1.89 pg/ml and an alternative mean of 19.33, assuming that the standard deviation is 5.56 pg/ml.

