For TBARS, conventionally treated CBSDH patients had a mean TBARS of 2.92 ± 0.38 nmols/ml compared with mean TBARS of 2.23 ± 0.33 nmols/ml in controls. When the sample size is 8, a single group t-test with a 0.05 two-sided significance level will have 99% power to detect the difference between a null hypothesis mean TBARS of 2.23 nmols/ml and an alternative mean of 2.92, assuming that the standard deviation is 0.38 nmols/ml.

Analysis plan: The mean, median, standard deviation, and 95% confidence intervals for TNF- α and TBARS will be generated.

B. Does taurine decrease the primary outcome biomarkers of TNF- α and TBARS?

Sample size and statistical power consideration: We hypothesize that taurine treatment will decrease oxidative stress and inflammation in CBSDH patients, which will be evaluated by comparing the levels of TBARS and TNF- α after 4 hours and 4 days on taurine compared to the corresponding baseline levels (before treatment). The minimum number of evaluable patients on high dose taurine therapy is eight, but can be as high as 10. Eight evaluable baseline paired samples provide 80% or higher power to detect an effect size in the range of 1.2-1.5, which is the standardized (by the standard deviation of the changes) mean difference between the alternative hypothesis of reduced oxidative stress/inflammation due to taurine therapy and the null hypothesis of high oxidative stress/inflammation before taurine treatment. A paired t-test was used for the calculation with a one-sided significance level of 0.05.

Power	Effect Size
0.95	1.30
0.9	1.15
0.8	0.98

To translate the effect size into the actual detectable level of the two markers, preliminary data showed a mean baseline TNF- α of 19.33 ± 5.56 pg/ml in treated CBSDH patients. Assume the correlation coefficient (Rho) of TNF- α between baseline and 4 days (or 4 hours) on taurine therapy is in the typical range of 0.1-0.5, and the variance of TNF- α on four days (or 4 hours) at taurine therapy time points are the same as at the baseline, then the detectable mean value of TNF- α at 4 days (or 4 hours) on therapy is 12.0 (for Rho=0.1)-13.9 (for Rho=0.5) with 80% power. Similarly, mean baseline TBARS of 2.92 ± 0.38 nmols/ml were observed in CBSDH (treated) patients, assume that taurine can reduce TBARS level, the detectable mean value of TBARS at 4 days (or 4 hours) on therapy is 2.42 (for Rho=0.1)-2.55 (for Rho=0.5) with 80% power.

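### Question A compares TBARS and TNF-α with control, but its analysis plan names no test; the sizing test treats the preliminary control mean as a known constant, which matters for TBARS.

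*Combined protocol and SAP*

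**What the plan says.** Section 5.K, part I, names TBARS and TNF-α as the primary efficacy parameters and puts two questions to each. Question A is "Is the biomarker elevated in the untreated patient compared to control", and its purpose is given as "This question is required to validate the preliminary data".

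The sizing text uses a single-group t-test at two-sided 0.05 with 8 patients. For TBARS this test "will have 99% power to detect the difference between a null hypothesis mean TBARS of 2.23 nmols/ml" and an alternative of 2.92 with SD 0.38. For TNF-α the null is the preliminary control mean of 1.89.

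The analysis plan for question A is one sentence covering both markers: "The mean, median, standard deviation, and 95% confidence intervals" are to be produced. It gives no test, comparator or difference from control. For question B, by contrast, the plan names its test: "One-sample t-test will be used to test if the changes are significantly different from zero". That test concerns change from baseline and cannot answer question A.

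The TBARS null comes from Section 4 ("versus controls 2.23 ± 0.33 nmols/ml"). The N = 10 printed there is not assigned to patients or to controls. Section 5.J.2 says that reference values exist for almost all measurements, but gives no source or size for TBARS. The enrolment criteria admit only patients with the disease, so no concurrent control group is planned.

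**The concern.** Question A compares two populations, and the control level is itself an estimate. A test that fixes it at 2.23 counts the sampling error of the patient mean and ignores that of the control mean. The planned 95% interval for the patient mean does not help: it excludes 2.23 exactly when the single-group test rejects. If TBARS were judged this way, the false-positive rate would exceed the nominal 5%, and the interval would be too narrow to describe a difference from control. This bears on a primary marker and on a question whose stated role is to confirm earlier data.

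**Working it through.** **Inputs.** TBARS: control mean 2.23, SD 0.33; treated patients mean 2.92, SD 0.38 (Sections 4 and 5.K). Poorly treated patients: "4.08 ± 0.56 nmol/ml in un- or poorly treated" (Section 4). TNF-α: patient SD 5.56, control SD 0.53. Patients: 8, the planning number; Section 5.D allows up to 16 exposed and analysed. Control number: not stated, so taken as 5, 10, 20 and 40.

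**Step 1: the stated power.** d = (2.92 − 2.23)/0.38 = 1.816. Noncentrality = 1.816 × √8 = 5.14 on 7 df. Power at two-sided 0.05 = 99.2%, which agrees with the stated 99%. The control SD of 0.33 does not enter.

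**Step 2: what is left out.** Standard error of the patient mean: 0.38/√8 = 0.134. Standard error of the control mean with 10 controls: 0.33/√10 = 0.104. Standard error of the difference: √(0.134² + 0.104²) = 0.170.

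**Step 3: error rate with the control mean fixed.** When there is no true elevation, the single-group statistic is distributed as k × t(n − 1), with

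k = √[1 + (0.33²/n_c)/(SD_p²/n)].

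The two-sided error is P(|t(n − 1)| > t_crit/k), where t_crit is 2.365 for n = 8 and 2.131 for n = 16.

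| Patient SD | Patients | Controls | k | Two-sided error |
|---|---|---|---|---|
| 0.38 | 8 | 5 | 1.486 | about 15.6% |
| 0.38 | 8 | 10 | 1.266 | 10.4% |
| 0.38 | 8 | 20 | 1.141 | 7.7% |
| 0.38 | 8 | 40 | 1.073 | 6.3% |
| 0.56 | 8 | 10 | 1.130 | 7.5% |
| 0.38 | 16 | 10 | 1.486 | 17% |

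Half of each figure is false elevation, against a nominal 2.5%. The SD 0.56 row matters because Section 5.K says: "The proposed study will include mostly patients who are untreated or poorly treated". More patients make the error worse, because the patient standard error shrinks while the ignored control error does not.

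For TNF-α with 8 patients and 10 controls, k = √[1 + (0.53²/10)/(5.56²/8)] = 1.004 and the error is 5.1%.

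**Step 4: the Welch test instead** (simulation, normal data, 2.92/0.38 against 2.23/0.33, two-sided 0.05).

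| Patients | Controls | Welch power |
|---|---|---|
| 8 | 5 | 86% |
| 8 | 10 | 96% |
| 8 | 20 | 98% |
| 8 | 40 | 99% |
| 16 | 10 | 99.6% |

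With 8 patients and 10 controls, the Welch error rate under no elevation is about 4.9%. The mean interval half-width is 0.361 nmol/ml against 0.307 for the patient-only interval (ratio 1.18). With 20 controls the ratio is 1.07.

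**Step 5: how often the verdict changes.** With 8 patients, 10 controls and the planning SDs, the smallest significant difference is 0.318 for the single-group test and 0.365 for Welch (14 df). The two therefore part only for an observed patient mean between about 2.55 and 2.59. In simulation they disagree in 1.6% of trials at 2.92/0.38 with 10 controls, in 0.3% with 20 controls, and in essentially none at 4.08/0.56 with 10.

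**The case against.** The strongest reply is that the error rates describe a method the analysis plan never adopts. The fixed 2.23 appears only in the sizing text, and other sections speak generally of comparison with normal values. This stands, so every figure in Step 3 is conditional. It does not remove the gap: either the sizing test is the intended analysis, with the error rates shown, or a primary question has no stated test.

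Second, the size depends on a control number that the documents do not give. That also stands. A reader might take the N = 10 in Section 4 as the control number and quote 10.4% as the error rate, but the text does not assign that N to a group. With a large reference set the inflation is small.

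Third, testing a small rare-disease cohort against a historical benchmark is a recognised approach, and the verdict would seldom change. The second part stands at the planning effect. The first holds where the benchmark is a fixed target, whereas question A asks about elevation relative to control.

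A reader might also infer that the 99% is a miscalculation or that 8 patients are too few. Neither follows: the figure is correct for the test it describes, and Welch power is 96% or more with 10 or more controls. Nor is TNF-α distorted in the same way. It shares the missing test, but the ignored control error is trivial beside the patient spread.

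**Conclusion.** The specification gap is established for both markers: question A has no stated test and no planned estimate of the difference from control. The numerical consequence is confined to TBARS and arises only if patients are judged against 2.23 as a constant. On that condition, with 8 patients at SD 0.38, the two-sided error lies between about 6.3% (40 controls) and 15.6% (5 controls). It is lower at SD 0.56 and higher with more patients. These figures assume normal data, the preliminary SDs and an assumed control number. The documents do not show that the trial would reach a wrong conclusion: their own data point to real elevation, and at the planning effect with 10 controls the two tests nearly always agree. Question B is unaffected. The plan should be changed because the correction is cheap, but the point does not threaten the design.

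**What to change.** For both markers, state the control set in Section 5.K: source, assay, mean, SD and number. Analyse question A with a two-sample Welch t-test at two-sided 0.05, and report a 95% confidence interval for the patient-minus-control difference. Control summary statistics are enough.

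Restate the TBARS power as conditional on both sample sizes: with 8 patients, about 86%, 96%, 98% and 99% with 5, 10, 20 and 40 controls; above 99% with 16 patients and 10 controls.

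If the preliminary controls are reused, do not describe the result as independent validation of the control level. Welch corrects the error rate but still rests on the same control mean.

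The cost is wording and retrieval of the control summary data. With 8 patients and 10 controls the interval is about 18% wider and the stated power falls by about 3 points. No extra patients are needed if there are about 10 or more controls.
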